6.3.3.10. Counting rules for combining solicited and unsolicited adverse events

For output combining solicited and unsolicited adverse events, all serious adverse events will be considered systemic events since the administration site flag is not included in the expedited adverse event CRF pages. Unsolicited adverse events with missing administration site flag will be considered systemic.

Solicited events will be coded by MedDRA as per the following codes:

Solicited event	Lower level term code	Corresponding Lower level term decode
Pain	10022086	Injection site pain
Redness (Erythema)	10022061	Injection site erythema
Swelling	10053425	Injection site swelling
Fever	10016558	Fever
Headache	10019211	Headache
Fatigue	10016256	Fatigue
Myalgia	10028411	Myalgia
Arthralgia	10003239	Arthralgia

Note that these codes might be adapted depending on the current version of MedDRA at the time of analysis.

Multiple events with the same preferred term which start on the same day are counted as only one occurrence.

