4.3.2. Main analytical approach

4.3.2.1. Safety analysis

The estimand analysis for safety will be performed on the ES for participants in Part A and Part B. For the analysis of solicited events, the daily assessment from the investigator (either to correct the participant entry or to replace a missing participant entry) will take precedence over the participant's entry only when the investigator assessment is done up to 36 hours after 23h59 of the specified day.

Descriptive analysis by group will be summarized as follows:

- The safety follow-up time will be tabulated using descriptive statistics (mean, median, minimum, maximum), including the percentage of participants with at least 6 months safety follow-up post-vaccination.
- The number and percentage of participants with at least one administration site event (solicited and unsolicited), with at least one systemic event (solicited and unsolicited) and with any AE (solicited and unsolicited) during the 4-day and the 30-day follow-up period after vaccination will be tabulated with exact 95% CI. The same computations will be done for Grade 3 AEs, for Grade 3 non-serious AEs and for AEs resulting in a medically attended visit. Those analyses will present all solicited and unsolicited AEs, including SAEs (unless otherwise specified).
- The number and percentage of participants with at least one administration site event (solicited only), with at least one systemic event (solicited only) and with any solicited event during the 4-day follow-up period (i.e., the day of study intervention administration and 3 subsequent days) after vaccination will be tabulated with exact 95% CI. The same computations will be done for Grade 3 AEs and for AEs resulting in a medically attended visit.
- Compliance in completing solicited events information will be tabulated (See Section [6.2.2](#)).
- The number and percentage of participants reporting each individual solicited administration site or systemic event (any grade, Grade 3 and resulting in medically attended visit) during the 4-day follow-up period after vaccination will be tabulated with exact 95% CI. If the proportion of participants who completed the eDiary entries from Day 1 through Day 4 is below 90%, the outputs will also be tabulated for these participants only (see Section [6.2.2](#)).

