- The verbatim reports of unsolicited AEs, including SAE and AESI, will be reviewed by a qualified person and the signs and symptoms will be coded according to the MedDRA Dictionary for Adverse Reaction Terminology. Every verbatim term will be matched with the appropriate Preferred Term.
- The number and percentage of participants with at least one report of SAE classified by the MedDRA Primary SOC, HLT and PT from vaccination up to study end (6 months after study intervention administration) will be tabulated with exact 95% CI.
- The number and percentage of participants with at least one report of SAE classified by the MedDRA Primary SOC, HLT and PT, related to study intervention administration, from vaccination up to study end (6 months after study intervention administration) will be tabulated with exact 95% CI.
- The number and percentage of participants with any fatal SAE, from vaccination up to study end (6 months after study intervention administration) will be tabulated with exact 95% CI.
- The number and percentage of participants with at least one report of pIMD classified by the MedDRA Primary SOC, HLT and PT from vaccination up to study end (6 months after study intervention administration) will be tabulated with exact 95% CI.
- The number and percentage of participants with at least one report of pIMD classified by the MedDRA Primary SOC, HLT and PT, related to study intervention administration, from vaccination up to study end (6 months after study intervention administration) will be tabulated with exact 95% CI.
- All SAEs, pIMDs and AFs from vaccination up to study end (6 months after study intervention administration) will also be described in detail in a tabular listing.
- AEs/SAEs leading to study discontinuation from vaccination up to study end (6 months after study intervention administration) will be tabulated.

- For web posting purposes, the number of occurrences and the number and percentage of participants with non-serious AEs (solicited and unsolicited combined) during the 30-day follow-up period will be produced by SOC and PT.
- In case of pregnancies, these will be described in detail in a tabular listing.
- AF AESIs will be tabulated within the summary of AEs or SAEs according to their classification.

Refer to Section 6.1.5 and Section 6.1.6 for the analysis of concomitant medications and concomitant vaccination.

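### In the combined adverse-event table, SAP 6.3.3.10 counts an unsolicited serious injection-site reaction as systemic instead of administration-site

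*SAP*

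**What the plan says.** SAP 6.3.3.10 opens by limiting its own scope: "For output combining solicited and unsolicited adverse events". Within that scope it sets two defaults. For serious events, "all serious adverse events will be considered systemic events since the administration site flag is not included in the expedited adverse event CRF pages". For the rest, "Unsolicited adverse events with missing administration site flag will be considered systemic".

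The output that splits pooled events by location is the overall table in SAP 4.3.2.1. It counts participants "with at least one administration site event (solicited and unsolicited), with at least one systemic event (solicited and unsolicited", and participants with any AE, over 4 days and over 30 days. It has further versions for Grade 3, Grade 3 non-serious and medically attended events. On serious events the section says: "Those analyses will present all solicited and unsolicited AEs, including SAEs (unless otherwise specified".

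Two other tables in the same section also split events by location but do not pool. One counts participants "with at least one administration site event (solicited only), with at least one systemic event (solicited only". The other counts participants "reporting each individual solicited administration site or systemic event (any grade, Grade 3 and resulting in medically attended visit".

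On coding of unsolicited events, SAEs included, SAP 4.3.2.1 says: "Every verbatim term will be matched with the appropriate Preferred Term".

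**The concern.** The rule settles where a reaction occurred by whether a case report form page has a field for it. The reason given is a gap in data collection, not a view that serious events are systemic by nature. The resulting error runs one way: a local event can move to the systemic row, but a systemic event cannot move to the local row through this rule. Among unsolicited local reactions it always catches the serious ones.

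At stake is one descriptive table, but that table is the only planned administration-site summary that includes unsolicited events. The unsolicited and SAE tables are organised by system organ class, high level term and preferred term, with no local/systemic split.

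The Grade 3 and Grade 3 non-serious versions show a side effect. For unsolicited events their administration-site rows cannot differ, because no SAE record can enter either one. A reader could take that agreement as evidence that no serious Grade 3 local reaction occurred, when the counting rule produces it.

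**Working it through.** **Inputs**

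- Counting rule and its scope: SAP 6.3.3.10.
- Tables, periods and versions: SAP 4.3.2.1.
- Solicited local events are pain, redness and swelling: Protocol 10.3.3, Table 21.
- A solicited-type event with onset outside the solicited period is unsolicited: Protocol 10.3.4.
- All solicited events on Days 1-4 go into the eDiary whatever their intensity: Protocol 10.3.5.1.
- Planned sizes: 425 per cohort in Part A, and 1025 at-risk participants in Cohorts 1 and 3 combined (425 + 600): Protocol 4.1 and SAP 5.

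**Step 1: trace each kind of local reaction through the combined table**

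| Local reaction | Record | Administration-site row | Systemic row |
|---|---|---|---|
| Serious, not a solicited type, onset Days 1-4 | SAE page | Not counted | Counted, 4-day and 30-day |
| Serious, any type, onset Days 5-30 | SAE page | Not counted | Counted, 30-day only |
| Serious, solicited type, onset Days 1-4 | eDiary and SAE page | Can count through the eDiary | Can also count through the SAE record |
| Non-serious, unsolicited, flag missing | AE page | Not counted | Counted |
| Non-serious, unsolicited, flag present | AE page | Counted | Not counted |

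The first, second and fourth lines follow directly from the rule. The third is a reading. SAP 6.3.3.10 counts same-day events with the same preferred term once, but does not say which location class survives when one record is from the eDiary and the other is an SAE.

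These rows count participants with at least one event. In the first, second and fourth cases the participant drops out of an administration-site row only if no other local event puts them in that row for the same period and version. They are new to the systemic row only if no other systemic event already puts them there.

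**Step 2: the plan's nearest figure**

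No stated number bears directly on this rule. The nearest is the probability of seeing at least one participant with an AE among 1025, which is 1 - (1 - p)^1025:

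- p = 0.1%: 1 - 0.999^1025 = 64.1% (stated 64%)
- p = 0.2%: 1 - 0.998^1025 = 87.2% (stated 87%)
- p = 0.3%: 1 - 0.997^1025 = 95.4% (stated at least 95%)

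The stated figures reproduce. If the affected reactions had a true rate of 0.1%, which is an assumption, the chance of seeing none would be 100% - 64.1% = 35.9%.

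**Step 3: size per case**

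- At-risk group, Cohorts 1 and 3: 1/1025 = 0.098%, about 0.10 point
- Older group, or Cohort 1 alone in a Part A analysis: 1/425 = 0.235%, about 0.24 point

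SAP 6.3.4.1 shows percentages to one decimal, so one case can be visible.

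**Step 4: illustration on an assumed rate**

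The documents give no Grade 3 administration-site rate. Assuming about 1%, one lost case changes the row as follows (Clopper-Pearson 95% CI):

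- N = 1025: 10 participants, 0.98% (0.47 to 1.79), becomes 9, 0.88% (0.40 to 1.66)
- N = 425: 4 participants, 0.94% (0.26 to 2.39), becomes 3, 0.71% (0.15 to 2.05)

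The shift is small against the width of either interval.

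**The case against.** The strongest defence is that this is a prespecified, disclosed convention with a stated reason, that it contradicts nothing else in the plan, and that it loses no safety information. Every SAE is tabulated by preferred term and listed in detail. Unsolicited AEs, SAEs included, are tabulated by preferred term in any-grade, Grade 3, related and medically attended versions. A serious injection-site reaction coded to a site term is therefore visible elsewhere. The combined location table is not among the analyses in Protocol 9.3.2. The reactogenicity endpoint itself is served by the per-event solicited table, which the rule does not touch. The Grade 3 non-serious version leaves SAEs out, so the SAE default cannot alter it. All of this stands, and it keeps the point minor. It does not make the row assignment correct.

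Three stronger readings are tempting, and the documents support none of them.

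- *All administration-site counts are affected.* The rule's opening words confine it to pooled output.
- *Serious local reactions are removed from the local counts.* That does not hold in general for Day 1-4 pain, redness or swelling, however extensive. The eDiary record exists, and nothing in the rule deletes it.
- *Grade 3 local events are understated by 5% to 20%.* That range needs an assumed 1-2% rate (10 to 20 of 1025) and an assumed one or two misplaced cases: 1/20 = 5%, 2/10 = 20%. Neither input is in the documents, and a serious event need not be Grade 3 (Protocol 10.3.5.2).

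It is also fair to object that coding does not settle every case. A reaction coded as plain cellulitis carries no site information.

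**Conclusion.** The point holds, confined to the combined 4-day and 30-day table. There the rule misplaces unsolicited serious site reactions, and unsolicited site reactions with a missing flag, always in the same direction. For a solicited Day 1-4 reaction that is also an SAE, the finding is only that the SAP does not specify how the two records are counted.

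The effect on any row is at most one participant per case, and the number of cases may be zero. The per-case percentages rest on the planned group sizes. No rate of serious or unflagged site reactions is available from which to project a total. The primary immunogenicity objectives and their hypothesis tests are untouched. This is a minor improvement, worth making because the preferred-term coding already planned can correct most of the error.

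**What to change.** In SAP 6.3.3.10, replace the two defaults with one rule. SAEs, and unsolicited AEs with a missing flag, are classed as administration-site when their MedDRA term is on a prespecified list of injection, vaccination and administration site terms, and as systemic otherwise. Fix the list before database freeze. The section already maps solicited pain, redness and swelling to injection-site terms, so the approach is not new to it.

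Add a sentence on how an eDiary record and an SAE record of the same reaction are counted, including which location class applies.

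The cost is a short SAP amendment, one coding look-up and a brief medical review of non-specific terms such as cellulitis. No case report form change is needed. If the sponsor keeps the present rule, the minimum is a footnote to the combined table that states the convention and names any SAE with a site term by its preferred term.

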6.3.3.11. Counting rules for occurrences of solicited events

When the occurrences of solicited events are summarized, each event recorded as having occurred during a specific period will be counted as only one occurrence regardless of the number of days on which it occurs.

The intensity of administration site redness/swelling and fever will be scored as follows:

Intensity grade	Redness/Swelling	Fever
0	≤ 20 mm	$< 38.0^{\circ}\text{C}$ (100.4°F)
1	$> 20 - \leq 50$ mm	$\geq 38.0^{\circ}\text{C}$ (100.4°F) - $\leq 38.5^{\circ}\text{C}$ (101.3°F)
2	$> 50 - \leq 100$ mm	$> 38.5^{\circ}\text{C}$ (101.3°F) - $\leq 39.0^{\circ}\text{C}$ (102.2°F)
3	> 100 mm	$> 39.0^{\circ}\text{C}$ (102.2°F)

6.3.4. Display of decimals

6.3.4.1. Percentages

Percentages and their corresponding confidence limits will be displayed with one decimal except for 100% in which case no decimal will be displayed.

6.3.4.2. Demographic/baseline characteristics statistics

The mean, median, and standard deviation for continuous baseline characteristics (height, weight, BMI, pre-dose body temperature) will be presented with one decimal.

The minimum and maximum values and quartile values (if required) will be presented with the same number of decimals as the observed values.

The maxima and minima of transformed height/weight variables will be displayed without decimals.

The maximum and minimum of transformed body temperatures will be displayed with one decimal.

6.3.4.3. Serological summary statistics

For each assay, GMTs and their confidence limits will be presented with one decimal, as well as GMT fold increase from pre-vaccination.

GMT group ratios and their confidence limits will be displayed with 2 decimals regardless of the actual values.

CCI

